## **Effect mechanism of custom-made foot orthoses on foot pronation subjects and chronic low back pain: a randomized controlled trial**

Study Design: Double blinded Randomized controlled trial.

### Clinical Relevance

Custom-made foot orthoses may contribute to improving chronic low back pain. This question represents an important benefit for patients and for the public health system by reducing expensive treatments, such as surgery or long periods of rehabilitation.

Keywords Low back pain, foot, pronation, posture, custom-made foot orthoses.

NCT number NCT03996980

Date: 4/02/2019

## **Methods**

### Design

A double-blinded two-arm randomized controlled trial. The participants were randomly allocated to a custom-made foot orthoses intervention group or a placebo orthoses intervention group.

This paper was written according to the CONSORT 2010 Statement guideline for reporting randomized clinical trials (Schulz KF, Altman DG, Moher D, CONSORT Group.

## Recruitment

The trial was conducted between January 2019 and September 2019. The participants were between 18 and 65 years old with a diagnosis of nonspecific CLBP and pronated foot ( $FPI \geq +6$ ) recruited from the Podiatry Clinic of the University of Seville. Potential participants were initially interviewed briefly to be evaluated in the participation in the study (a qualified podiatrist carried out this initial assessment). The original sample consisted of 105 subjects (54 women and 51 men), 53 corresponding to the experimental group and 52 to the control group. After finishing the follow-up period, there was a loss of 4 subjects (who left the study for unknown reasons or because it was impossible to contact them).

## Inclusion Criteria

The inclusion criteria were: Males and females between 18 and 65 years old, presence of CLBP, Foot Posture Index pronated in one or both feet (henceforth,  $FPI) \geq +6$ .

## Exclusion Criteria

The exclusion criteria were: serious illness, current participation in another research study, pregnancy, previous back or foot surgery, current treatment of foot pathology or back, and leg length discrepancy  $> 5$  mm.

## Procedure

We recruited 105 patients of the Podiatry Area of the University of Seville. There was a routine biomechanical lower limb examination to determine the inclusion criteria (Figure 1). A [podiatrist](#) assessed the foot posture during the biomechanical assessment based on the six-item foot posture index ( $FPI \geq +6$ ). The FPI consists of six validated

items measured in a standing relaxed position of the subject; The categories are:

Supinated foot: -1 a -12.

Neutral foot posture: 0 to +5 (neutral).

Pronated foot posture: +6 to +12.

[figure not shown]
The patients were randomized to either an experimental treatment group or a control group. The main researcher and the participants were blind to which group and kind of treatment was being studied. The random allocation to each group was done by a collaborating researcher who generated the random sequence ( blocked randomization based on a random numbers table) and the treatment was administered (experimental/control).

The primary outcome was measured at the moment of inclusion in the study, and after four weeks of use of the orthose treatment. We used the Oswestry Disability Index Questionnaire (ODI) for Lower Back Pain which provides information on disability due to CLBP and its impact on ten daily activities and a 100 mm visual analogue scale (VAS). At the end of the study the control group received the custom-made foot orthoses best suited to them.

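### One researcher made the blocked sequence and also allocated, with no concealment step described: does the plan need to change?

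*Combined protocol and SAP*

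**What the plan says.** All of the relevant text is in two sections of the combined protocol and SAP.

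- **Procedure, allocation:** "The random allocation to each group was done by a collaborating researcher who generated the random sequence", and the method is "blocked randomization based on a random numbers table". The same sentence goes on to say, in the passive, that treatment was given, without clearly naming who gave it.
- **Procedure, blinding:** "The main researcher and the participants were blind to which group and kind of treatment was being studied". The collaborating researcher is not listed as blind.
- **Procedure, eligibility:** "There was a routine biomechanical lower limb examination to determine the inclusion criteria". A podiatrist scored foot posture at that examination, and randomization is described afterwards.
- **Procedure, baseline:** "The primary outcome was measured at the moment of inclusion in the study" and again after four weeks. Whether the first measurement came before the assignment was known is not stated.
- **Recruitment:** for the first interview, "a qualified podiatrist carried out this initial assessment". The arm sizes are given as "53 corresponding to the experimental group and 52 to the control group", follow-up is described as finished, and 4 participants were lost.

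No readable section mentions envelopes, central allocation, a separate holder of the list, a block size, or a rule that enrolment is final before assignment. A figure placed just before the randomization text could not be read.

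**The concern.** Generating the sequence and assigning from it are usually kept in different hands. With both in one pair of hands, the next assignment is known to the assigner before the next patient is entered. If that person could also admit, defer or turn away patients, the arms could differ in prognosis from the outset, and blinding afterwards would not repair this.

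The stakes would be real here. The outcomes are the Oswestry disability questionnaire and a visual analogue pain scale, both self-reported. The Statistical analysis section describes a t test or Mann-Whitney comparison with no baseline adjustment, so a difference created at entry could carry into the estimate.

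**Working it through.** The plan gives no figure on this point, so the check is mainly a reading of the text, with a little arithmetic.

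**1. What selection bias needs.** Two conditions must both hold: (a) someone knows or can predict the next assignment, and (b) that person can affect entry or its order.

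| Condition | What the document says | Status |
|---|---|---|
| (a) Foreknowledge | The collaborating researcher made the list and assigned from it | Possible for all 105 assignments |
| (b) Influence on entry | Screening and foot-posture scoring are tied to a podiatrist; the eligibility examination is narrated before randomization; the main researcher is blind | Not shown, and not expressly excluded |

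The document never says that the collaborating researcher recruited, screened or enrolled anyone. Nor does it say that this person and the podiatrist were different people.

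**2. Counts.** Allocated: 53 + 52 = 105. Lost: 4. Remaining: 105 − 4 = 101, which equals the target in the Statistical analysis section.

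**3. Does the split reveal the block size?** Write 105 as full blocks of even size b plus a remainder r:

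- b = 2: 52 × 2 + 1
- b = 4: 26 × 4 + 1
- b = 6: 17 × 6 + 3
- b = 8: 13 × 8 + 1
- b = 10: 10 × 10 + 5
- b = 20: 5 × 20 + 5

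Because 105 is odd and b is even, r is always odd and at most b − 1. Full blocks balance exactly, and the last part-block can split with a difference of 1. So 53/52 fits every even size from 2 to 20. It is evidence neither for nor against concealment.

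**4. Would knowing the block size matter?** For a person holding the list, all 105 assignments are known whatever the block size. Block size matters only to someone without the list who sees past assignments. In a fixed block of size 2m, the expected number of assignments already forced by earlier ones is 2m/(m + 1). Under assumed sizes (the document gives none):

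- size 2: 52 × 1 = 52
- size 4: 26 × 4/3 = 34.7
- size 6: 17 × 1.5 = 25.5

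These figures concern a different person from the one in question, and they do not measure bias in this trial.

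**5. Is any assignment left to protect?** The cover date, 4/02/2019, lies inside the stated trial period whether read as February or April ("The trial was conducted between January 2019 and September 2019"), which might suggest that enrolment was still open. But the Recruitment section gives final arm sizes, finished follow-up and losses. On the document's own account, the number of assignments still to be made is 0.

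**The case for a change.** The strongest case for acting runs as follows. Blinding after assignment is not concealment before it. The podiatrist is never said to be a different person from the allocator. Entry leaves room for judgement: there is a brief interview, serious illness is an undefined exclusion, and the presence of chronic low back pain has no stated threshold. A 53/52 split shows balanced numbers, not balanced prognosis. Asking for a few sentences of explanation, or an acknowledged limitation, costs almost nothing.

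Most of this stands as a description of what the text leaves out. The block size, the holder of the list, the person who enrolled, and the order of baseline measurement and assignment are all unstated, and the risk is not excluded. What does not follow is that the design was defective. Silence about concealment is not evidence that it was absent, and the separation the text does show points away from an allocator who chose patients. A separate list-maker, sealed envelopes and randomly varied blocks would be sensible in a trial about to start. Here they would apply to nobody. The lack of baseline adjustment is a separate matter of analysis and does not make the allocation more or less concealed.

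**Conclusion.** No change to the plan is needed. The document omits detail about allocation that a reader would want, but it does not show that the allocator could influence entry, and followed in the natural way (a third party allocating people already found eligible) the procedure gives sound results.

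On size: one list governed all 105 assignments, the bias, if any, cannot be estimated from the document, and no assignments remain to which a different procedure could apply.

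This rests on two assumptions: that the collaborating researcher had no part in screening or enrolment, and that the Recruitment section's account of completed follow-up is correct despite the cover date. The trial team can settle the first from its own records when it reports who enrolled, who held the list, the block size, and whether baseline scores preceded assignment. If concealment could not be confirmed, possible selection bias would be a limitation on the conclusion. The design and the analysis would stay as they are.

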#### Statistical analysis

The recruitment target was 101 participants (G\* Power 3.0.10, Franz Faul, Universität Kiel, Germany). Based on a preliminary study the sampling size necessary was 36 participants in each group. This size was increased to compensate for possible alterations in the statistical significance of the results caused by potential participant dropouts. Therefore, we used a final sample size of a total of 101 participants.

The Student's t test was used for the comparison between means and medians of the groups. Whenever a normally distribution pattern was rejected, the nonparametric Mann-Whitney U test was applied. Secondary outcomes were tested for differences by Pearson's Chi or Student's t-tests.

All analyses were performed using SPSS® version 24.0. A P-value <0.05 was set as statistically significant.

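### ODI and VAS both sit, unranked, under one singular primary outcome, and the plan has no order, adjustment or joint rule for the two tests

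*Combined protocol and SAP*

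**What the plan says.** Combined protocol and SAP, Procedure section. The outcome is introduced in the singular: "The primary outcome was measured at the moment of inclusion in the study, and after four weeks of use of the orthose treatment". The sentence that follows names the instruments: "We used the Oswestry Disability Index Questionnaire (ODI) for Lower Back Pain which provides information on disability due to CLBP", then, joined to it, "and a 100 mm visual analogue scale (VAS"). Neither is called primary or secondary by name, and they are not ranked.

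Statistical analysis section. Three statements bear on the point:

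- Sample size: "the sampling size necessary was 36 participants in each group". The outcome, effect size, standard deviation and power behind this figure are not given.
- Tests: Student's t, or Mann-Whitney if normality is rejected, not tied to a named outcome. Then "Secondary outcomes were tested for differences by" chi-squared or t-tests, with no secondary outcome named anywhere.
- Threshold: "A P-value <0.05 was set as statistically significant". Sidedness is not stated. No testing order, adjustment or rule requiring both instruments appears.

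**The concern.** The trial has two arms and one follow-up time, so its main conclusion rests on these two instruments. Followed as written, the plan produces two unadjusted tests of the primary question at 0.05 each. It does not say what is concluded if one is significant and the other is not, and either could then be presented as the primary result. Whether 0.05 is the error rate of the main conclusion depends on a rule that is not written down.

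The sample-size statement would normally settle which instrument drives the trial. Here it cannot, because it names no outcome.

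**Working it through.** **Inputs from the document.** Threshold 0.05 and 36 per group (Statistical analysis). Allocation: "53 corresponding to the experimental group and 52 to the control group"; attrition: "After finishing the follow-up period, there was a loss of 4 subjects" (both Recruitment). Hence 53 + 52 − 4 = 101, which equals the stated final sample size. The split of the 101 is not given; it lies between 53 v 48 and 49 v 52.

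**Assumptions, because the document is silent.** Two-sided tests; ODI-VAS correlation ρ from 0 to 0.9; 80% or 90% power behind the 36.

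**The plan's own figure.** The 36 per group cannot be reproduced without an outcome, effect size and power. It can only be solved backwards: a two-sample t test with 36 per group at two-sided 0.05 has 80% power at d = 0.67 and 90% power at d = 0.775.

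**Step 1. Error rate if either result counts.** With no effect on either scale,

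P(at least one P<0.05) = 1 − P(|Z₁|<1.96 and |Z₂|<1.96).

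At ρ = 0 this is 1 − 0.95² = 0.0975. Since P(either) + P(both) = 0.05 + 0.05, the chance that exactly one is significant is 2 × P(either) − 0.10. Holm requires the smaller P to be below 0.025, so its error rate is the same expression with 2.24 in place of 1.96.

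| ρ | Either at 0.05 | Exactly one at 0.05 | Holm, any false claim |
|---|---|---|---|
| 0 | 0.0975 | 0.095 | 0.049 |
| 0.5 | 0.091 | 0.082 | 0.047 |
| 0.7 | 0.084 | 0.067 | 0.043 |
| 0.9 | 0.070 | 0.041 | 0.036 |

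Counting only false results that favour the orthoses, the either rule gives 4.9% (ρ = 0) to 3.5% (ρ = 0.9), against 2.5% for one test.

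**Step 2. Error rate under the other two rules.** With one named primary it is 0.05. If both must be significant, it does not exceed 0.05 in any configuration. Neither rule inflates it.

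**Step 3. What Holm costs.** Power with 101 participants; simulated rows use t tests at 51 v 50, ρ from 0 to 0.9.

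| Rule | d = 0.67 | d = 0.775 |
|---|---|---|
| Single primary at 0.05 | 91% | 97% |
| Holm, each instrument, same effect on both | 89-91% | 96-97% |
| Holm, at least one, same effect on both | 90-98% | 96-99.7% |
| Holm, only one instrument responds | about 86% | about 94.5% |

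The last row is essentially the power of one test at 0.025. It rounds to the same values for 53 v 48, 51 v 50 and 49 v 52. When both instruments respond Holm does better than this, because the second is tested at 0.05 once the first is rejected.

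**The case against.** The strongest reply is that the document is less ambiguous than it may look. Only two instruments are named as outcome measures, and both follow directly on the sentence about the primary outcome. Secondary outcomes are handled separately, with a chi-squared test that suits categorical variables rather than two continuous scales. This is a fair argument, and it makes *both are primary* the natural reading. A reader might go further and infer that the primary outcome is wholly unidentified; the text does not support that. The reply is not conclusive either, since the outcome is singular and t-tests are also listed for secondary outcomes. Nor does it remove the point: if both are primary, a decision rule is needed, and there is none.

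A second reply is that no sentence says success on either scale is enough. That is correct. A reader might infer that the trial runs at a 9.75% error rate. The document does not support that: the figure needs an either rule, two-sided tests and zero correlation, and pain and disability in the same back-pain patients are unlikely to be uncorrelated.

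A third reply is that a ranking may exist elsewhere. That cannot be judged from this document, which only shows that no ranking is given here.

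**Conclusion.** The point holds as a gap in the decision rule. Two instruments share one singular primary outcome, each would be tested at 0.05, and the plan does not say how the two results combine. If either counts as success, the false-positive chance is 7.0% to 9.75% for assumed correlations of 0.9 to 0, two-sided, with the upper end unlikely. If one is primary or both are required, there is no inflation.

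A reader might also infer that the choice was left open so that it could be made after seeing the results. The document does not show this. It is dated 4/02/2019 yet reports recruitment to September 2019 and the losses in the past tense, so it does not settle what had been seen when it was written. The power figures rest on the assumed 80% or 90% behind the 36 per group and, where stated, on an equal effect on both scales. The correction should be made, but the gap does not invalidate the trial.

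**What to change.** Add one or two sentences to the Statistical analysis section.

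1. If a choice documented before results were seen by group exists (for example, the outcome used for the 36 per group), name that instrument as the single primary, test it at two-sided 0.05, and make the other secondary.
2. Otherwise keep ODI and VAS both as primary and apply Holm: claim the one with the smaller P if it is below 0.025, and then the other if it is below 0.05. Label any later ranking of the two as post hoc.

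No extra participants or data are needed. Under route 1, the cost is that a result on the other instrument is secondary only. Under route 2, the smaller P must reach 0.025. On the assumptions above, that costs at most about 2 percentage points of power per instrument when both respond equally. If only one responds, power falls from 91% to about 86% (d = 0.67) or from 97% to about 94.5% (d = 0.775).

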#### Fabrication of foot orthoses

Molds of both feet were obtained for all the participants . The phenolic foam molds were made in a condition of the participant's feet under weight-bearing. The feet were manipulated before being introduced into the phenolic foam placed in a neutral position. We obtained a positive mold of the feet filling the phenolic foam molds with liquid plaster. The positive mold was used to make the custom orthoses of polypropylene of 3-

mm (heated to 180°C) from the heel to just behind the metatarsal heads, covered with a 2-mm thick polyethylene foam layer of 35-shore in the experimental group. For the control group, placebo treatment, a flat insole was made of polyester resin adjusting it to the size of the foot, but not adapting it, the aim being not to alter the patient's normal function (Figure 1).

[figure not shown]
**Figure 1.** Foot orthoses.

#### Statistical analysis

The recruitment target was 101 participants (G\* Power 3.0.10, Franz Faul, Universität Kiel, Germany). Based on a preliminary study the sampling size necessary was 36 participants in each group. This size was increased to compensate for possible alterations in the statistical significance of the results caused by potential participant dropouts. Therefore, we used a final sample size of a total of 101 participants.

The Student's t test was used for the comparison between means and medians of the groups. Whenever a normally distribution pattern was rejected, the nonparametric Mann-Whitney U test was applied. Secondary outcomes were tested for differences by Pearson's Chi or Student's t-tests.

All analyses were performed using SPSS® version 24.0. A P-value <0.05 was set as statistically significant.

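### Baseline ODI and VAS are collected but not used: only unadjusted tests are named, and week-4 versus change scores is left open

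*Combined protocol and SAP*

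**What the plan says.** The Procedure section fixes two measurement times: "The primary outcome was measured at the moment of inclusion in the study, and after four weeks of use of the orthose treatment". It then names two instruments: "We used the Oswestry Disability Index Questionnaire (ODI) for Lower Back Pain" and "a 100 mm visual analogue scale (VAS".

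The Statistical analysis section is the whole analysis plan. For the group comparison it states "The Student's t test was used for the comparison between means and medians of the groups". The fallback is "Whenever a normally distribution pattern was rejected, the nonparametric Mann-Whitney U test was applied". For the rest, "Secondary outcomes were tested for differences by Pearson's Chi 2 or Student's t-tests". Significance is set at P < 0.05, without saying whether tests are one- or two-sided.

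No section mentions a covariate, ANCOVA, regression or a mixed model. No section says whether the groups are compared on the week-4 score or on the change from inclusion.

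**The concern.** Two linked gaps have one remedy.

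- **The analysis is not fixed.** A t test on week-4 scores and a t test on change scores both fit the text. Their estimates differ by exactly the chance baseline difference between the arms, so the same data can give two answers. If the choice is made after results are seen, the 5% error rate no longer holds.
- **Precision is given away.** Week-4 scores ignore the baseline. Change scores subtract all of it, however weakly it predicts the outcome. ANCOVA estimates how much to subtract. The Mann-Whitney fallback is unadjusted as well.

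Bias is not at issue: randomisation makes either unadjusted comparison valid if it is fixed in advance.

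**Working it through.** **The plan's own figure.** The Statistical analysis section says "the sampling size necessary was 36 participants in each group", raised to 101 in total. Effect size, SD, power and sidedness are not stated, so 36 can be neither confirmed nor refuted. Solved backwards for a two-sided 5% test with 80% power, d = √2 × (1.960 + 0.842)/√36 = 0.66 by the normal formula and 0.67 by the t distribution. With 90% power it is about 0.775. These are used below only as possible effect sizes.

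**Inputs.** From Recruitment: 53 and 52 randomised, 4 lost, leaving 101. Assumed: a 51/50 split (any split of the 4 losses gives much the same result), equal SDs at both visits, and r = 0.3, 0.5 or 0.7.

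**Precision.** Variance of the group difference, relative to week-4 scores:

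- week-4 score: 1
- change score: 2(1 − r) = 1.40, 1.00, 0.60
- ANCOVA: 1 − r² = 0.91, 0.75, 0.51

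Estimating the slope multiplies the ANCOVA standard error by √(1 + 1/(101 − 4)) = 1.005.

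| ANCOVA SE relative to | r = 0.3 | r = 0.5 | r = 0.7 |
|---|---|---|---|
| week-4: √(1 − r²) × 1.005 | 0.959 | 0.870 | 0.718 |
| change: √((1 + r)/2) × 1.005 | 0.810 | 0.870 | 0.927 |

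Against week-4 scores, ANCOVA breaks even where 1 − r² = 97/98, that is at r = 0.101. At r = 0 its standard error is 0.5% larger.

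**Chance imbalance.** The SD of the baseline difference D, in outcome SDs, is √(1/51 + 1/50) = 0.199. The median absolute value is 0.6745 × 0.199 = 0.134, and the 95% range is ±0.39. Given D, the week-4 comparison shifts by rD and the change comparison by −(1 − r)D. For D = 0.134 the week-4 shift is 0.04, 0.07 or 0.09 SD; for D = 0.39 it is 0.12, 0.20 or 0.27 SD. These shifts are the source of the extra variance above, not a second harm.

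**Power and disagreement.** Simulated with 51 against 50, two-sided 5%. Here d = 0.563 is the difference for which the week-4 test has 80% power at 101. Disagreement means that exactly one of the week-4 and change tests gives P < 0.05.

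| | r = 0.3 | r = 0.5 | r = 0.7 |
|---|---|---|---|
| d = 0.563: week-4 power | 80% | 80% | 80% |
| d = 0.563: change power | 66% | 80% | 95% |
| d = 0.563: ANCOVA power | 83% | 90% | 97% |
| d = 0.563: disagreement | 27% | 23% | 20% |
| d = 0.67: week-4 power | 92% | 92% | 92% |
| d = 0.67: ANCOVA power | 93% | 97% | 99.6% |
| d = 0.67: disagreement | 18% | 12% | 9% |

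**Type I error.** Under no effect each test alone rejects in about 5% of trials. The two test statistics have correlation √((1 − r)/2) = 0.592, 0.500, 0.387. From the bivariate normal, the chance that at least one gives P < 0.05 is 8.8%, 9.1% or 9.4%; simulation agrees to within about 0.3 percentage points.

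**Why ANCOVA settles the choice.** With baseline in the model, using the change score instead of the week-4 score alters only the baseline coefficient (by −1). The treatment estimate, interval and P value are identical.

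**The case against.** The strongest reply is that nothing here is invalid and the gain may be small. That stands in part.

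- **Size of the effect.** If 36 per group meant 90% power (d about 0.775), week-4 power at 101 is already 97%, ANCOVA adds 1 to 3 points, and disagreement falls to about 10%, 5% or 3%. The documents do not exclude this.
- **Equal SDs.** The change-score figures depend on this assumption. At r = 0.5 and d = 0.563, a baseline SD of 0.8 or 1.25 times the week-4 SD moves change-score power from 80% to about 87% or 69%, and disagreement from 23% to about 17% or 32%. The ANCOVA against week-4 comparison is unaffected.
- **The 9% is conditional.** It needs a choice made after seeing results, and nothing in the documents shows that one was made. Naming either reading would remove it without ANCOVA.
- **Limits of the remedy.** ANCOVA does not decide whether ODI or VAS is primary; the Procedure section speaks of one primary outcome and then names both. A switch triggered by non-normal residuals would also repeat the data-driven step already in the plan.
- **Timing.** The date under Clinical Relevance is 4/02/2019, but Recruitment states "The trial was conducted between January 2019 and September 2019" and reports losses after follow-up. A new prespecified analysis may no longer be possible.

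These points limit the size of the gain and shape the fix. They do not close the gap: the endpoint form is unstated at any r, and baseline data already in hand go unused.

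**Conclusion.** The concern holds, as one of precision and specification rather than validity. The plan should be changed on this point, though the planned tests are not wrong in themselves. At r = 0.5, ANCOVA cuts the standard error by 13% against either reading; over r = 0.3 to 0.7 the cut is 4% to 28% against week-4 scores and 19% to 7% against change scores. Leaving the reading open allows a false-positive rate of about 9% if it is chosen after the results. The calculations assume r, equal SDs at the two visits and a 51/50 split. The power gain is modest if the true difference is 0.67 SD or more, and there is no gain over week-4 scores if r is below about 0.10.

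**What to change.** **If outcome data have not been seen:** for each outcome, state one main analysis: ANCOVA with the week-4 score as response, randomised arm as factor and the baseline score of the same instrument as covariate. Report the adjusted mean difference with 95% CI and P value. Fit it for ODI with baseline ODI and for VAS with baseline VAS, and say separately which of the two is primary. Replace the switch to an unadjusted Mann-Whitney test with one baseline-adjusted alternative named in advance. A bootstrap interval for the adjusted difference, reported alongside in every case, needs no trigger and keeps the same estimate; a rank-based ANCOVA is possible but does not give an adjusted mean difference. Keep the unadjusted test as supporting, and say whether it uses week-4 or change scores.

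**If outcome data have been seen:** keep the described test, state which score it used, and show ANCOVA beside it labelled post hoc.

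**Cost:** no new data, one degree of freedom, a little analysis work and, if r is near zero, a standard error about 0.5% larger than for week-4 scores.

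### For the implied primary outcome (ODI and VAS) the plan sets no effect measure, confidence interval or baseline adjustment, leaves open 4-week score or change, and lets an unspecified normality check pick the test

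*Combined protocol and SAP*

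**What the plan says.** The analysis plan is the short Statistical analysis section. Its main comparison reads "The Student's t test was used for the comparison between means and medians of the groups", followed by "Whenever a normally distribution pattern was rejected, the nonparametric Mann-Whitney U test was applied". Secondary outcomes have their own sentence, which begins "Secondary outcomes were tested for differences by Pearson's Chi" and also allows t tests. The only criterion for a result is "A P-value <0.05 was set as statistically significant".

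The Procedure section says "The primary outcome was measured at the moment of inclusion in the study, and after four weeks of use of the orthose treatment". Its next sentence begins "We used the Oswestry Disability Index Questionnaire (ODI) for Lower Back Pain" and adds a 100 mm VAS. Neither instrument is expressly named as the primary outcome. That the t/Mann-Whitney rule governs ODI and VAS is therefore an inference, drawn from this adjacency and from the separate sentence on secondary outcomes.

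The document does not state:
- which normality check is used, at what level, or on which variable
- whether 4-week scores or changes are compared
- what effect measure or confidence interval accompanies the test
- what use, if any, is made of the baseline value

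The Design section cites a reporting guideline, but that sentence fixes no estimate for this trial.

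**The concern.** A plan that fixes only a P value does not tell the reader in advance what quantity measures benefit, or how precisely it will be known. Here a baseline value of the same score is collected, yet no use of it is specified, so precision available from data in hand may be lost.

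The wording is also wrong on one point: Student's t test compares means, not medians.

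The switch adds a lesser problem. Under a pure shift between arms, the t test and Mann-Whitney address the same null. If the arms differ in shape or spread, they answer different questions: Mann-Whitney asks whether one arm tends to have lower scores, which need not coincide with a lower mean. Because the checked variable is not named, the text does not determine which of the two tests would be reported.

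**Working it through.** **Inputs.** The Recruitment section gives 53 + 52 = 105 randomized and "After finishing the follow-up period, there was a loss of 4 subjects", leaving 101. Losses by arm are not given, so 51 and 50 is assumed. The documents give no mean, SD or baseline correlation for ODI or VAS, so these are assumed over ranges, with both scores taken as 0-100. The plan has no effect estimate or interval to reproduce. Its 36 per group comes without power, difference or SD, so it cannot be rebuilt, and this point does not alter it.

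**1. Precision without adjustment.** Half-width = t(0.975, 99) × SD × √(1/51 + 1/50), which is about 1.984 × SD × 0.199.
- SD 10: 3.95
- SD 15: 5.92
- SD 20: 7.90
- SD 25: 9.87

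At SD 15 a just-significant difference has an interval from 0 to 2 × 5.92 = 11.8 points.

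**2. Precision with baseline adjustment.** ANCOVA multiplies the half-width by about √(1 − r²). At SD 15:
- r = 0.3: 5.92 × 0.954 = 5.65
- r = 0.5: 5.92 × 0.866 = 5.13
- r = 0.7: 5.92 × 0.714 = 4.23

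**3. The switch, if 4-week scores are tested.** Simulation with beta-distributed scores and equal true means. The check is assumed to be Shapiro-Wilk in each arm at 0.05, with Mann-Whitney if either arm is rejected and the t test otherwise. There were 10,000 runs per case (Monte Carlo SE about 0.2 points at 5%). Entries are the percentage of trials with P<0.05.

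| Mean | SD 15/15 | 15/17 | 14/17 | 13/17 | 12/18 | 12/20 |
|---|---|---|---|---|---|---|
| 50 | 5.0 | 5.0 | 5.1 | 4.8 | 5.9 | 5.4 |
| 40 | 5.3 | 5.4 | 5.3 | 5.8 | 5.8 | 6.0 |
| 30 | 5.3 | 5.7 | 6.2 | 6.3 | 8.4 | 10.8 |
| 25 | 5.4 | 5.7 | 6.6 | 7.5 | 10.7 | 15.2 |
| 20 | 5.0 | 6.3 | 8.0 | 10.3 | 15.8 | 25.9 |

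Of the 25 unequal-SD cases, 16 are at or below 7%. Over those 25, the t test rejects in 4.7-5.7% and ANCOVA with HC3 standard errors (baseline correlation 0.5) in 4.3-5.3%.

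**4. Direction.** The excess almost always favours the wider arm. In a 3,000-run repeat at mean 30, SD 12/20, 9.4 of 11.1 percentage points did so. At mean 25, SD 12 vs 18, the medians are 23.6 (narrow) and 21.4 (wide), and the probability that a wide-arm score is the lower of a pair is 0.538, although the means are equal.

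**5. The same rule on change scores.** With baseline mean 40, SD 15, correlation 0.5 and 3,000 runs per case, rejection at SD 12/18 and 12/20 was:
- mean 30: 4.6% and 4.7%
- mean 25: 5.8% and 5.8%
- mean 20: 5.1% and 5.7%

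A further repeat gave about 5-6.5%.

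**6. Which test gets reported.** With identical arms, baseline mean 40, 4-week mean 30, SD 15 and correlation 0.5 (3,000 runs), the switch fired in 56% of trials if 4-week scores were checked per arm, 72% if pooled, and 10% if changes were checked per arm. The two per-arm checks disagreed in 54% of trials.

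**7. Power of the proposed analysis** (HC3 ANCOVA against Mann-Whitney, at r = 0.3, 0.5, 0.7).
- Beta, 30 vs 22, SD 15: 78.0, 85.4, 94.9% against 80.0, 80.3, 78.6%
- Gamma (shape 3), shift 6: 75.5, 82.6, 93.5% against 81.3%
- Beta, 40 vs 32, SD 15 (near-symmetric): 78.6, 85.6, 95.4% against 74.7, 75.6, 74.9%

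At r = 0.3 the differences are 78.0 − 80.0 = −2.0, 75.5 − 81.3 = −5.8 and 78.6 − 74.7 = +3.9 points.

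**The case against.** The strongest reply is that the switch does little harm, and this largely stands. With identical arms the rule rejects in 5.0-5.4% of trials. The larger rates need equal means with clearly different SDs, low scores, and a test on 4-week scores. On change scores, an equally open reading of the plan, they essentially disappear. If the orthosis arm were the narrower one, the excess would mostly run against the treatment.

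A reader might go further than the documents allow in three ways:
- *The switch generally creates false claims of benefit.* The figures above do not show that.
- *A response in only some participants could produce a significant result without a mean benefit.* If some improve and the rest are unaffected, the mean is lower, so there is a mean benefit. The equal-means cases require others to worsen enough to cancel the gain.
- *The plan ignores the baseline.* It may compare changes, which would use baseline, though not as a covariate. The text supports only that no use is specified.

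It can also be said that ANCOVA is partly a preference, and that an effect measure, an interval and a named check would meet much of the complaint. That is fair. The case for ANCOVA is that the baseline score is already collected and that one sentence also settles the choice between score and change. The half-widths show what an interval would convey; they do not show that any conclusion was wrong.

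**Conclusion.** The point holds as a cheap improvement. Its substance is the missing baseline-adjusted estimate with an interval. Without it, the plan promises a P value where, at the assumed SD 15, the unadjusted uncertainty is about 6 points either way, and it leaves unclaimed a narrowing of roughly 5% to 29% (1 − √(1 − r²) for r from 0.3 to 0.7). The switch alone is a minor, conditional issue and would not carry the point.

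The absence of an effect measure, an interval and a named variable is plain from the text and needs no assumption. Every figure for size rests on assumed distributions, SDs, correlations, numbers per arm and form of normality check. Application to the primary outcome is inferred. Confidence in the size is therefore moderate.

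**What to change.** In the Statistical analysis section, delete the reference to medians and remove the normality-triggered switch for the primary outcome. State that, for ODI and for VAS, the primary analysis is the between-group difference in mean 4-week score from ANCOVA adjusted for the baseline value of the same score, with heteroscedasticity-robust standard errors and a 95% confidence interval. This also settles 4-week score versus change. Keep Mann-Whitney on the 4-week score as a labelled sensitivity analysis that cannot replace it.

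The Recruitment and Statistical analysis sections describe follow-up and analysis in the past tense. Label the change post hoc unless it can be shown to precede sight of results by arm. If that cannot be shown, report the test as the plan now states it alongside the adjusted difference and its interval.

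The cost is two sentences, a little more analysis and no new data, with possibly two results side by side. Removing the switch gains no power by itself; the gain comes from baseline adjustment and depends on a correlation that the documents do not give. In skewed data with correlation about 0.3, ANCOVA can have 2-6 percentage points less power than Mann-Whitney. At 0.5 and 0.7 it had more in every case examined.
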